and replication, a former cornerstone of the scientific method, has now been largely superseded by single large multinational studies. This lack of replication[18] as well as concerns of possible interactions between studies drug intervention and different healthcare systems can result in residual uncertainties even following “positive” results from large, single, comparative RCT evaluations[11, 12]. Conventional RCTs also have important limitations including inclusion/exclusion intricacies with recruitment difficulties, complexities in implementation, incomplete follow-up (especially for side effects) and high cost[17]. These limitations often reduce the feasibility of performing RCTs in everyday practice with a consequence that many routine practices are never fully evaluated or confirmed. While non-experimental methodologies can provide information in a more cost-efficient manner, the associated uncertainties, often principally but by no means limited to confounding by indication bias, is such that the gold standard design for drug assessment remains randomization. The “trick” to increasing RCTs is to employ both novel RCT designs and analytical elements to address these barriers and make trials more clinically and economically feasible.

As individual randomization may be difficult in situations where there are many clinicians involved in patient care and when rapid access to care is a priority, we have elected to use the novel pragmatic RCT cluster randomization (CR) design. This design resolves these issues and enhances practicality, efficacy, and bias reduction. A variation of the parallel group CR design is the cluster randomized crossover (CRXO) design which will control any temporal trends which might occur, for example with the rapidly evolving PCI technology. We are therefore proposing a CRXO design whereby a single center will perform 6-10 cluster periods each of 2 months duration during which all patients will receive one of the two allotted treatments regimes.

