The CRXO design will simplify trial conduct, enhance overall recruitment, and generalizability while maintaining study integrity. The merits of the CRXO design have been increasingly appreciated with recent publications in several high impact journals[19, 20]. RCTs with individual randomization is logistically difficult in situations where there are many acute caregivers and where patients may be recruited in a 24X7 emergency environment as with ACS. CR, by simplifying the mechanics of randomization, avoids these problems as well as the potential bias of cross contamination while maintaining the integrity of randomization. Given that the division of cardiology (Chief of Cardiology support letter in the Appendix) has agreed that equipoise exists regarding these competing interventions, all patients who are candidates for DAPT will be eligible for the study. Also CRXO importantly portends that individual informed consent for an ACS trial can be obtained in a less urgent setting, permitting more detailed information sharing and a more thorough and meaningful researcher / patient dialogue to occur.

A CR trial usually requires a larger sample size to achieve the same power as a standard RCT due to possible correlated measures with the clusters, measured by the intraclass correlation coefficient (ICC). In our trial, the marked increased recruitment possibilities will more than compensate for this minimally decreased power. The CRXO design increases efficiency over standard CR studies. and importantly controls for any secular trends in concomitant therapies. CR trials do have diminishing returns in power and precision as cluster size increases but this may be mitigated by increasing the number of clusters as with a CRXO design[21]. The CRXO design can achieve up to 50% better power than the standard CR design[22]. Analyses must also account for the clustering to avoid the bias of overly precise estimates of the treatment effect.

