All patients hospitalized for an ACS, with or without ST-segment elevation, will be eligible to participate. For STEMI and NSTEMI positive biomarkers and appropriate ECG changes will be required. NSTEMI patients with negative biomarkers are generally considered as unstable angina and will also be eligible for study inclusion if their treating physician has determined that DAPT is appropriate. It is important to note that the entrance criteria of this study are well aligned with those of PLATO allowing synthesis of the totality of the evidence (see analysis section below).

The intervention

Patients will be randomly assigned to receive standard doses of ticagrelor or clopidogrel. Ticagrelor will be given according to PLATO dose[9] of a 180 mg loading dose followed by 90 mg BID. Clopidogrel patients will receive a 300-mg loading dose followed by 75 mg daily. All patients will receive aspirin loading dose of 325 mg followed by 81 mg daily. Patients will be encouraged to take their DAPT medication for 12 months. Patient compliance will be monitored electronically via the provincial drug formulary. This will allow for the assessment for any specific DAPT interactions, particularly with anticoagulants. This is of clinical importance since bleeding is the main adverse outcome associated with DAPT.

[figure not shown]
Study outcomes

The main outcome will be a composite of total mortality, myocardial infarction (MI), or stroke at 12 months (PLATO primary outcome). Secondary outcomes will be cardiovascular mortality, stroke, major bleeding requiring hospitalization, recurrent coronary revascularizations, patient compliance and drug side effects. Clinical events will be independently assessed from hospital and provincial electronic health records which have been previously validated for these outcomes[25-27]. Data extraction will be by blinded observers so the initial unblinding of treatment assignment should not result in bias. At the time of consent, patients

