will also be consented to consult their electronic health records at 1 and 3 years post randomization. The ability to measure long term outcomes at 3 years, via electronic databases, is another distinctive aspect of the study and will offer a unique opportunity to assess the long term consequences of different DAPT strategies following an ACS. While the main objective of this project is the evaluation of clinical effectiveness and safety outcomes, the expertise of the team will permit future ancillary investigations into quality of life and economic sub-studies. The project will also provide unique training and research opportunities for graduate students.

Sample size calculations

As there is some similarity between individuals within the same cluster, both within the same time period and across different time periods, CR trials require an increased sample size compared to a standard individual parallel group RCT. This loss of efficiency is more than offset by a more comprehensive patient recruitment. In addition to effect size and variation, CRXO sample size calculation depends upon the number of clusters, the size of the clusters, the number of time periods, and the similarity between individuals (both within and between clusters) as measured by the ICC. Assuming the event rates recorded in PLATO (12% vs. 10%), type 1 and type 2 errors of 5% and 20% respectively, power calculations for a standard individual randomized trial approach would suggest the need for 1,500 patients in each arm. For a CR trial, calculations using R (library(CRTsize) suggests that we need 6 clusters of 400 patients for each arm (total 4800, larger sample size due to ICC). However CRXO design has been shown to increase the statistical efficiency over the standard CR design[22]. The Figure below shows that 5 clusters for each arm (total sample size 4000) will provide greater than 80% power[21], suggesting that our 18-month recruitment period will be sufficient. Given our current annual angiogram / PCI volume and with the expected additional 10% of potential recruited ACS patients coming from the hospital CCU without an angiogram, we should have the capacity to meet our power calculations within an 18 month recruitment period based on the excellent (>90%) recruitment rates observed in other pragmatic comparative effectiveness trials[36].

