In addition to a standalone analysis, our main Bayesian analysis will incorporate the 1800 PLATO NA patients as our prior distribution, essentially providing a > 50% safety margin for our sample size calculations (see next section).

Statistical analysis

[figure not shown]
The trial data will be analyzed following the intention to treat principal. Clustered data require appropriate advanced statistical techniques that accounts for the likeness of cluster members, otherwise analysis can lead to overly precise estimates and potentially incorrect inferences about the effectiveness of the intervention.

Appropriate analysis will involve generalized estimating equations and hierarchical models. Bayesian analyses will be performed using JAGS [37] version 3.4.0 and R [38]. All Markov Chain Monte Carlo simulations will be run on two chains with 10 000 iterations discarding the first 1000. Convergence will be monitored using CODA [39] and checked by observing the traces of posterior samples, and by inspecting the Gelman-Rubin R statistic [40] and the Raftery-Louis diagnostics.[41]

Our primary analysis will involve a Bayesian approach that synthesizes all the pertinent evidence concerning these DAPT regimes by incorporating our prior information (PLATO data) with the likelihood of the current data. The advantages of this approach include a mathematically rigorous and exact combination of the totality of the data allowing direct probability statements about the relative strengths of the two regimes (statements that are desired by clinicians and decision-makers but which are technically impossible with the usual frequentist (p value) approach). The strength of this approach is displayed graphically and is described more fully in the next section. We will also perform a “standalone” Bayesian analysis by using a non-informative prior so that results driven uniquely by the data from this proposal may be appreciated.

Anticipated results and conclusions

Concretely the question remains which PLATO data shall we use for the prior data, the whole dataset or that limited to the NA subgroup. Our Bayesian approach will examine the robustness of the data by considering both! First, consider in the Figure (top) what might be called the “enthusiastic” prior which uses all the data and shows the overall benefit with ticagrelor.

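### Eligibility asks only that a patient be a candidate for DAPT, not suitable for both study drugs, although each open 2-month period gives every patient a single drug

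*Protocol*

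**What the plan says.** Three parts of the protocol bear on who enters and what they receive.

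- **Entry.** Methods states that "all patients who are candidates for DAPT will be eligible for the study", on the ground that the cardiology division agrees equipoise exists between the two regimens. Study population states: "All patients hospitalized for an ACS, with or without ST-segment elevation, will be eligible to participate". The only individual clinical judgement there concerns biomarker-negative patients, who qualify "if their treating physician has determined that DAPT is appropriate". That judgement is about DAPT as a class.
- **Treatment.** Methods describes a single centre running 6 to 10 periods of 2 months, "during which all patients will receive one of the two allotted treatments regimes".
- **Safeguards.** Study outcomes says that data extraction will be blinded, "so the initial unblinding of treatment assignment should not result in bias". Statistical analysis says: "The trial data will be analyzed following the intention to treat principal". The risk section (Possible problems) relies on randomisation to balance the arms at baseline.

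Methods adds that consent can be sought after the acute phase. Ethics says that every patient's explicit consent will be requested and describes the risk as minimal because both arms are standard care.

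**The concern.** Eligibility is set at the level of the drug class, while treatment is set at the level of the individual drug, by the calendar. The two fit together only for patients who could take either drug. For a patient suited to just one, the text leaves two outcomes:

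1. Followed to the letter, the patient is assigned an unsuitable drug whenever the period happens to be the wrong one. The minimal-risk statement in Ethics does not fit that patient.
2. If the clinician leaves the patient out instead, this happens in one type of period only and with the drug known. The same kind of patient enters in the other type of period, and the arms are then drawn from somewhat different populations.

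The second outcome matters for the primary comparison, because none of the stated safeguards acts on who is entered.

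**Working it through.** The protocol gives no figure for this point, so the check is first a reading and then an illustration of size.

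**Is there a rule requiring suitability for both drugs?** The places where one could stand are:

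| Place in protocol | What it settles | Suitability for both drugs required? |
|---|---|---|
| Methods, eligibility sentence | DAPT candidates enter | No |
| Methods, equipoise | Agreed by the division for the two regimens | No; it does not address the individual patient |
| Study population | ACS inpatients enter; physician judges DAPT if biomarkers are negative | No |
| Study population, PLATO comparison | Entry criteria described as close to PLATO's | No; no exclusion is listed or adopted |
| The intervention | Doses, and a plan to look at anticoagulant interactions | No |

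**Do the safeguards reach selective entry?**

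- Blinded extraction protects how outcomes are recorded. It does not affect which patients are in the data.
- Intention to treat keeps entered patients in their assigned group. It cannot restore patients who never entered.
- Randomisation is of periods. Once a period's drug is known, it does not balance who is entered during that period.

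**How large could the effect be?** The inputs are:

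- Event rate 12%, and planned difference 12% − 10% = 2.0 points (Sample size calculations).
- f, the share of patients left out in ticagrelor periods only. This is assumed at 1%, 2% or 5%. The only bound is loose: the protocol's recruitment expectation is "based on the excellent (>90%) recruitment rates observed in other pragmatic comparative effectiveness trials", so under 10% would fail to enter for any reason, refusal included.
- k, the risk of those patients relative to the average of all patients. This is assumed at 0.5, 1 or 2.
- No true drug effect, and no opposite exclusions in clopidogrel periods.

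The event rate among patients entered in ticagrelor periods is

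rate = 12% × (1 − f·k) / (1 − f), and the false difference is 12% − rate.

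Worked cases at f = 5%:

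- k = 2: 12% × (1 − 0.10) / 0.95 = 11.37%, a difference of +0.63 points.
- k = 0.5: 12% × (1 − 0.025) / 0.95 = 12.32%, a difference of −0.32 points.

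| f | k = 2 | k = 1 | k = 0.5 |
|---|---|---|---|
| 1% | 11.88% (+0.12) | 12.00% (0) | 12.06% (−0.06) |
| 2% | 11.76% (+0.24) | 12.00% (0) | 12.12% (−0.12) |
| 5% | 11.37% (+0.63) | 12.00% (0) | 12.32% (−0.32) |

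Positive values falsely favour ticagrelor and negative values falsely favour clopidogrel. Relative to the planned 2.0 points, the range is −0.32/2.0 = −16% to +0.63/2.0 = +32%. Opposite exclusions in clopidogrel periods would partly cancel these differences.

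**The case against.** The strongest reply is that the protocol states nothing wrong here. The entry rule is the same in every period, so differential entry arises only if staff depart from it. Broad entry is also deliberate: Methods counts complicated inclusion and exclusion criteria among the weaknesses of conventional trials. Both drugs are accepted care, the division agrees on equipoise, each patient is asked for consent, and the entry population is said to resemble that of PLATO, which compared the same two drugs. The document nowhere says that patients suited to only one drug occur, or how often.

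Much of this stands. The rule is neutral between the drugs, and a reader who inferred that the design guarantees unequal arms would be going beyond the text. A reader might also take the anticoagulant sentence, "This will allow for the assessment for any specific DAPT interactions, particularly with anticoagulants", as the protocol's own admission that some patients suit only one drug. It does not show that. The reason given is bleeding under DAPT generally, and the sentence can equally mean an interaction in either arm.

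Two parts of the reply fall short. Divisional equipoise and resemblance to PLATO do not tell a clinician what to do with a patient who should not have the current period's drug. And leaving such a patient out is the natural clinical response to a rule that otherwise assigns an unsuitable drug, so it cannot be set aside as mere non-adherence. A single symmetric criterion does little harm to the aim of broad entry.

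Patients who decline consent because they know the period's drug are a separate route, which the change proposed here would not close.

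**Conclusion.** The point holds as a gap in the eligibility wording. No criterion in the document requires suitability for either drug, and the three stated safeguards do not cover a patient left out in one type of period with allocation known.

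Bias is possible but not demonstrated. The number of such patients, their risk, and the size and direction of any effect cannot be derived from the document. The illustrated range of −0.32 to +0.63 points passes through zero and rests wholly on assumed values of f and k and on one-sided exclusion. A reader might take the upper end, about a third of the planned difference, as an estimate. It is not one: it needs 5% of patients left out in ticagrelor periods only, all at twice the average risk.

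Dilution from later switching of drugs is ordinary in a pragmatic trial analysed by intention to treat and is not part of this point. This is a low-cost improvement, and the gap does not by itself undermine the design.

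**What to change.** In Methods and in Study population, state that a patient is eligible only if, on information available at presentation, there is no contraindication to ticagrelor or to clopidogrel. Judge this by one short prespecified list, applied identically in every period whatever drug is in use. Keep anticoagulant users, whom the protocol wants to study, unless they are unsuitable for one of the drugs. Keep patients who later switch in their assigned arm.

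As a secondary check, record counts and reasons for non-entry by period, so that the assumed balance can be examined. A list narrows clinical discretion without removing it, which is why the record is useful. The minimal-risk statement in Ethics would then apply to the population it fits.

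The cost is a sentence in two places, a short list and a simple log. The downside is slightly fewer eligible patients and slightly narrower generalisability.

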A major driver of standard RCT costs is the expense of securing long term follow-up. To overcome this barrier and the vexing potential bias of lost to follow-up, we will use the novel “randomized registry” design. An early example of this design involved a non-industry sponsored, multicenter, prospective, randomized, controlled, open-label clinical trial of manual thrombus aspiration in 7244 Swedish STEMI patients undergoing PCI[23]. In this remarkable trial, over 80% of all eligible patients were recruited and the trial took only 1 year to complete. The data were monitored and adjudicated as part of a regular registry validation. A NEJM editorial[24] called this the next disruptive technology in clinical research by allowing high quality trials to be successfully and rapidly completed at a small fraction of the usual cost.

Our study will employ baseline CRXO randomization (to avoid indication bias) with follow-up using the administrative database environment of the hospital electronic medical records and the universal Quebec healthcare system, which provides validated long-term follow-up of meaningful health outcomes of all patients[25-27] at minimal costs and with which the PI has a vast experience[28-31]. Moreover, these

databases will permit the acquisition of long term outcomes (beyond 12 months) which have been previously lacking in virtually all ACS trials. More specific details on patient side effects will be obtained via the hospital's electronic medical record and data warehouse which has been built using a CFI grant.

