Our proposed pragmatic, randomized – registry, cluster crossover randomized clinical trial is a novel design well suited to evaluating DAPT comparative effectiveness and addressing a pertinent patient orientated research question. The design can be seamlessly integrated into routine practice with minimal costs or ethical barriers, logistical feasibility, increased generalizability and enhanced capture of effectiveness and safety parameters. The proposed novel design and analysis of this trial will allow a timely answer to an important clinical question to be obtained in a very efficient manner at a small fraction ($<1/100$) of the cost of a standard RCT and a small fraction of the projected annual ticagrelor cost ($<1/1000$). While the main objective of this project is the evaluation of clinical effectiveness and safety outcomes, the structure of the project and the expertise of the team members will provide the data sources to permit later ancillary investigations into long term outcomes, quality of life, genomic and economic substudies. The project will also provide the first opportunity to look at long term comparative outcomes and will offer unique training opportunities.

Data analysis Amendment Oct 29 2019 While we obtain baseline patient information at the time of recruitment, follow-up data is obtained from the RAMQ provincial electronic records (patients sign consent at recruitment) as there are no follow-up direct patient visits with the research team. Historically we would apply to RAMQ and they would send us the follow-up data for consented patients. I was informed last week that this process has now been modified. Data will only be released to Centre d'accès aux données de recherche de l'Institut de la statistique du Québec (CADRISQ) and all analyses must be performed on their physical site. Therefore we must take our MUHC baseline data to CADRISQ, merge and then analyse the data at their site. Consequently I require an amendment to the protocol and a letter of authorization from the REB that I can submit to CADRISQ.

References

1. Antithrombotic Trialists C. Collaborative meta-analysis of randomised trials of antiplatelet therapy for prevention of death, myocardial infarction, and stroke in high risk patients. *Bmj.* 2002;324(7329):71-86. PubMed PMID: 11786451; PubMed Central PMCID: PMC64503.

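### Eligibility does not require provincial coverage, although follow-up rests largely, and compliance wholly, on provincial records

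*Protocol*

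**What the plan says.** **Who enters.** Protocol, Study population: "All patients hospitalized for an ACS, with or without ST-segment elevation, will be eligible to participate". Protocol, Methods, in the argument for the cluster crossover design: "all patients who are candidates for DAPT will be eligible for the study". Neither section, nor any other in the document, makes residence, provincial health insurance or drug-plan membership a condition of entry.

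**Where outcomes come from.** The sections differ:

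- Methods describes "follow-up using the administrative database environment of the hospital electronic medical records and the universal Quebec healthcare system", and says of the provincial system that it is one "which provides validated long-term follow-up of meaningful health outcomes of all patients".
- Study outcomes also names two sources: "Clinical events will be independently assessed from hospital and provincial electronic health records which have been previously validated for these outcomes".
- Data analysis Amendment Oct 29 2019 names one: "follow-up data is obtained from the RAMQ provincial electronic records (patients sign consent at recruitment) as there are no follow-up direct patient visits".

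**Where compliance comes from.** The intervention names one source: "Patient compliance will be monitored electronically via the provincial drug formulary". The same paragraph makes these data the basis for assessing interactions with anticoagulants. Compliance is a listed secondary outcome.

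The protocol does not say how a patient without a provincial record is classified, for events or for compliance.

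**The concern.** The design presents passive follow-up through administrative data as the answer to loss to follow-up. That works only if every enrolled patient is visible in the data for the full 12 months. A visitor or a resident of another province can meet the entry criteria and yet have no provincial file. A patient who moves away during the year has a file that stops. No study visit would reveal either case.

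In record-based follow-up an empty record looks the same as an event-free year. For drug use, someone whose prescriptions are not recorded by the provincial plan looks the same as someone who bought nothing.

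Three results are at stake:

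- **Event rates.** Both arms' absolute rates, and so the risk difference, would be too low.
- **Compliance.** It would be understated, and any between-arm difference would shrink by the same factor.
- **Anticoagulant interaction.** Anticoagulant users without plan records would be classed as unexposed.

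The section on possible problems defends the administrative databases as reliable for recorded drug exposure and outcomes. It does not ask whether every enrolled patient is in them.

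**Working it through.** **Inputs from the protocol.** Event rates of 12% and 10%, and a total of 4,000 patients, so 2,000 per arm (Sample size calculations).

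**Assumptions.** The protocol gives no uncovered share. Let *u* be that share, equal in both arms. Take *u* = 1–5% for health coverage and 10–50% for the drug plan, and true compliance of 80%. These values are illustrative.

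**1. Primary outcome, worst case.** Every event in an uncovered patient is missed and the patient is scored event-free. Observed rate = true rate × (1 − *u*).

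| *u* | Clopidogrel | Ticagrelor | Difference (points) | Risk ratio |
|---|---|---|---|---|
| 0 | 12.00% | 10.00% | 2.00 | 0.833 |
| 1% | 12 × 0.99 = 11.88% | 10 × 0.99 = 9.90% | 1.98 | 0.833 |
| 5% | 12 × 0.95 = 11.40% | 10 × 0.95 = 9.50% | 1.90 | 0.833 |

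The factor (1 − *u*) cancels in the ratio, so the relative effect is untouched while coverage is balanced.

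**2. Allowing for hospital records.** Suppose they capture half of the uncovered patients' events (an assumption). At *u* = 5% the effective loss is 2.5%: 12 × 0.975 = 11.70% and 10 × 0.975 = 9.75%, a difference of 1.95 points.

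**3. Power.** The protocol's figure of 1,500 per arm for individual randomization could not be reproduced: 12% versus 10%, two-sided 5%, 80% power needs 3,841 per arm. That is a separate matter. It means the baseline here must be computed rather than taken from the protocol. With 2,000 per arm, two-sided 5% and no allowance for clustering:

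- *u* = 0: 52.4%
- *u* = 5%, uncovered patients scored event-free: 50.2%
- *u* = 5%, uncovered patients excluded and not replaced (1,900 per arm): 50.4%

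Exclusion recovers about 0.2 points, so power is not the reason to act.

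**4. Unbalanced coverage.** With no true effect, and 5% uncovered in one arm against 7% in the other, the observed risk ratio is 0.93 / 0.95 = 0.979. Nothing in the protocol suggests such an imbalance.

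**5. Compliance, if no plan record is read as no purchase.** Observed compliance = 0.80 × (1 − *u*).

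| Share without drug-plan records | Observed compliance |
|---|---|
| 10% | 0.80 × 0.90 = 72% |
| 30% | 0.80 × 0.70 = 56% |
| 50% | 0.80 × 0.50 = 40% |

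No second source is named that could repair this.

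**The case against.** A reader might infer that the provincial databases are the only source of follow-up and that uncovered patients are counted as event-free and non-compliant. The documents support neither for events. Methods and Study outcomes both name hospital records beside provincial ones. The amendment names RAMQ alone, but its subject is where RAMQ data are released and analysed, and it does not withdraw the hospital source. No section states that an absent record is scored as a non-event or as non-compliance. That rule may sit in a statistical analysis plan that is not at hand.

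Four further points weigh on the other side:

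- **Linkage may expose the problem.** The amendment describes merging baseline data with the provincial data. A patient never insured in Quebec would normally appear as unmatched, not as matched with no events. This is fair for coverage at entry. It does not help with a patient who leaves during the year.
- **The group may be very small.** The protocol calls the health system universal and describes a regional referral population of about 1.5 million. Nothing in it shows how many patients lack coverage, and the drug-plan shares used above have no support in the text.
- **The relative effect is unaffected.** Clinical significance is defined relatively, as more than a 15% improvement, and the risk ratio does not move when coverage is balanced.
- **A condition may exist elsewhere.** The draft consent form in the Appendix cannot be seen.

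These points limit the size of the concern but do not remove it. Hospital records are only a partial backstop, because the recruiting centre takes referrals from 7–8 community hospitals and later events may present elsewhere. An analysis plan can set censoring rules and denominators, but it cannot change who was enrolled. For compliance the single-source reading is accurate.

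**Conclusion.** The point holds in a limited form. Entry is open to patients whom the main follow-up source, and the only compliance source, may not cover, so the claim of follow-up for all patients goes further than the eligibility rule allows. Absence of a record could be misread as absence of an event or of drug use; the documents do not show that it will be.

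For the primary outcome the effect is small: at an assumed 1–5% uncovered, 2.0 points become 1.98–1.90, with the risk ratio unchanged under balanced coverage. Those figures are the worst case for those shares, since they give hospital records no credit. The main exposure is in absolute event rates and, above all, in the compliance and anticoagulant-interaction results. There an assumed 80% reads as 72% at 10% without plan records, and lower if the share is larger. All shares are assumptions. This is an inexpensive improvement worth making, not a threat to the primary comparison.

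**What to change.** 1. Add valid Quebec health insurance at admission to the inclusion criteria. This is the part that belongs in the protocol.
2. Censor follow-up at the end of provincial coverage, using coverage dates in the linked file, so that no patient is carried as event-free to 12 months without being observable.
3. Compute compliance and drug-interaction results only in patients covered by the provincial drug plan, and state that denominator.
4. Report linkage rates by arm.
5. Reconcile Methods and Study outcomes, which name hospital and provincial records, with the amendment, which names RAMQ only.

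Items 2 to 4 may be placed in the protocol or the analysis plan.

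**Cost:** one inclusion line, the use of coverage dates, a few patients not enrolled, and a smaller, stated denominator for compliance. If the excluded patients are not replaced, power falls by about as much as it would have fallen through their missed events (50.4% versus 50.2% at 5% uncovered), so nothing is lost on the primary outcome.
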